#### 9.7. Adverse Event Reporting

All adverse events occurring during the trial must be documented in the CRF. This applies not only to those adverse events supposedly related to the study medication, but also to any undesired experience, whether or not a causal relationship is suspected.

For this, the CRF includes a specific section for collecting information related to the adverse events. In addition, for the serious adverse events, a standard Serious Adverse Event report form will be included.

#### 9.7.1 Serious Adverse Events

All serious adverse events will be reported by the investigator to the monitor responsible for the clinical trial or to the Pharmacovigilance Manager at Linical within 24 hours after their knowledge. Such report will be made by telephone, fax or email message. The Serious Adverse Event report form, duly completed, should be made available to the Pharmacovigilance Manager at Linical within 48 hours. The Medical Manager at Linical will review the reported documentation for any medical clarification.

Address and contact phone:

Amendment 04, Final Version 1.0
Protocol No.: BB-2001-201b
EudraCT No.: 2017-000877-35
Amendment 04, Final Version 1.0
07/Nov/2018
Page 77 / 142

Reporting time for the phone communication: 24 hours

Reporting time for the written report: 48 hours

#### 9.7.2 Non Serious Adverse Events

Non-serious adverse events will be documented in the specific section for reporting in the eCRF that will be submitted to BenevolentAI Bio once the participation of the subject in the clinical trial is completed.

#### 9.7.3 Data Monitoring Committee

No data monitoring committee will be used in this study.

Amendment 04, Final Version 1.0
Protocol No.: BB-2001-201b
EudraCT No.: 2017-000877-35
Page 78 / 142

#### 10.0 Protocol Deviations

#### 10.1. Protocol Deviations

Generally, a protocol deviation is not imperative for subject withdrawal. Before the statistical analysis begins, the protocol deviations must be taken into account for the population analysis. The mandatory withdrawal reasons will be considered as major protocol deviations. Other protocol deviations will be classified as minor protocol deviations. Additionally, the following major protocol deviations will be considered:

- 1) Violation of one of the inclusion/exclusion criteria after enrolment into the study.
- 2) Treatment incorrectly administered, or overdose.
- 3) Use of prohibited medication.

Any protocol deviation must be recorded in the eCRF.

#### 10.2. Procedure for protocol amendments

Any amendment to this protocol involving a substantial change may be made as an amendment or addendum in writing. In order to be formalised, it is necessary to obtain the agreement of all the responsible people who signed the original protocol.

Amendments that can result in substantial changes in the original protocol must be submitted and approved by the IRB/IEC and the Health Authorities.

Amendment 04, Final Version 1.0 07/Nov/2018 Page 79 / 142

#### 11.0 Statistical Methods and Determination of Sample Size

#### 11.1. Statistical and analytical plans

The statistical analysis will be performed by the Department of Biostatistics of Linical, using SAS® version 9.2 or later.

Statistical significance will be assessed for two-sided probability values < 0.05.

All descriptive variables will be tabulated. Quantitative variables will be described showing their number of available and missing observations, mean, median, standard deviation (SD), the range (minimum and maximum) and the first and third quartiles. Frequency and percentage will describe qualitative variables. Missing values will be tabulated with their frequency but will not be included in the calculation of percentages.

The main population for the efficacy analysis will be the intent to treat population (ITT). The per protocol population (PP) will be analysed also as a sensitivity analysis.

The main population for the safety analysis will be the safety population (SAF), defined as all the subjects who have received at least one dose of study treatment.

Full details of the statistical analysis will be given in a Statistical Analysis Plan (SAP) which will be prepared, approved and signed before the database closure, and so before the subjects' evaluability assessment.

Any deviation from the original SAP will be included and reported in the clinical study report (CSR).

#### 11.1.1 Data Sets Analysed

The safety population (SAF) will be defined as all subjects who have received at least one dose of the study treatment.

The intent to treat population (ITT) will be defined as all subjects who have taken at least one dose of study treatment and who have available a post-baseline evaluation of the primary efficacy endpoint at screening/baseline and at week 6.

The per protocol population (PP) will be defined as all subjects in the FAS who do not experience a major protocol deviation.

# 11.1.2 Demographic and Other Baseline Characteristics

Baseline characteristics (gender, age, race, weight, height, body mass index, blood pressure, heart rate) for the safety population will be summarised descriptively.

Categorical data will be summarised with absolute and relative frequencies (percentage), and numerical data will be summarised with the number, mean, median, standard deviation (SD), the range (minimum and maximum), and the first and third quartiles (if applicable).

Amendment 04, Final Version 1.0
Protocol No.: BB-2001-201b
EudraCT No.: 2017-000877-35
Page 80 / 142

#### 11.1.3 Efficacy Analyses

# 11.1.4 Primary Efficacy Analyses

ESS mean absolute change from baseline to the end of the 6-week treatment period will be analysed with an ANCOVA model, with the baseline ESS as a covariate, region and treatment as a factor. Missing data in the 6-week ESS evaluation will be considered as a treatment failure, that is imputing the missing ESS reduction as 0. Least-squared (LS) absolute mean changes will be presented by treatment group together with their corresponding 95% confidence interval. Paired-comparisons will be performed without any multiplicity adjustment.

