### 8.1. Inclusion Criteria

Subjects will be eligible for inclusion into the study only if all of the following criteria are met:

- (1) Signed informed consent (no study-related procedures may be performed before the subject has signed the consent form).
- (2) Subjects of either sex aged 50 to 80 years (both inclusive and relative to Day 1)
- (3) Subjects with previous diagnosis of Parkinson's disease (following the UK Parkinson's disease society brain bank clinical diagnostic criteria)\* of minimum 3 months before informed consent date.
- (4) Subjects capable of understanding and complying with protocol requirements
- (5) Subjects with medical history of excessive daytime sleepiness
- (6) Subjects with moderate or severe excessive daytime sleepiness indicated by an Epworth Sleepiness Score (ESS) > 12 at screening
- (7) Subjects with stable nocturnal sleep hygiene practices (e.g. temperature, darkness, quiet, place to lie down and stretch out) as per investigator's judgement
- (8) Male subjects who are nonsterilized and sexually active with a female partner of childbearing potential agree to use adequate contraception from signing of informed consent throughout the duration of the study and for 4 weeks after last dose\*\*
- (9) Female subjects of childbearing potential who are sexually active with a nonsterilized male partner agree to use adequate contraception from signing of informed consent throughout the duration of the study and for 4 weeks after last dose\*\*
- (10) Subjects on stable permitted concomitant medication for at least 4 weeks before screening.

Amendment 04, Final Version 1.0 07/Nov/2018 Page 44 / 142

- \* Additional details on the UK Parkinson's disease society brain bank clinical diagnostic criteria are included in Appendix 18.2.
- \*\* Definitions and acceptable methods of contraception, and Contraception and Pregnancy Avoidance Procedure and reporting responsibilities are defined in Section 8.4.1.8.

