# 8.4.1.14.1 Epworth Sleepiness Scale (ESS)

The Epworth Sleepiness Scale (ESS) is the primary efficacy endpoint and will be assessed at all study visits: screening, baseline (day -1), visit 2 (day 14), and visit 3 (day 42) or early termination.

The ESS is a self-administered questionnaire with 8 questions rated on a 4-point scale (0-3) for the assessment of the usual chances of dozing off or falling asleep while engaged in eight different activities. Most people engage in those activities at least occasionally, although not necessarily every day. The ESS score (sum of 8 item scores) ranges from 0 to 24, where the higher score corresponds to the higher average sleep propensity (ASP) in daily life (higher daytime sleepiness). The questionnaire takes no more than 2 or 3 minutes to answer and although the original language was English for Australia, this is validated in many different languages. All those validations were performed by Mapi Research Trust (https://eprovide.mapi-trust.org/instruments/epworth-sleepiness-scale#languages).

More information on the appropriateness of the ESS as the primary study endpoint is included in Section 7.2. An ESS sample questionnaire has been included in Appendix 18.2.

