### 8.4.2 Study Procedures

# Screening assessments (Day -28 to Day -8)

Subjects will be screened for enrolment within 3 weeks prior to the start of baseline assessments. Subjects will be screened in accordance with predefined entrance criteria as described in Sections 8.1 and 8.2. See Section 8.5.1 for the procedure for documenting screen failures.

Procedures to be completed at screening include:

- Subject information/Informed consent signed and dated.
- Assessment of inclusion / exclusion criteria.
- Demographics
- Medical history and previous medication (prohibited as of 4 weeks before D-28)
- Concurrent medical condition
- Physical examination
- Vital signs

Amendment 04, Final Version 1.0
Protocol No.: BB-2001-201b
EudraCT No.: 2017-000877-35
Page 59 / 142

- For women of childbearing potential the method of contraception must be documented (as CM as applicable)
- Laboratory (haematology, biochemistry), serum pregnancy test (for women of childbearing potential)
- Pharmacogenomic blood sample
- Electrocardiogram, heart rate, blood pressure
- Eye examination
- Cognitive assessment (MoCA)
- Columbia-Suicide Severity Rating Scale (C-SSRS)
- Fatigue assessment (FSS)
- Assessment of sleepiness scales: ESS
- Other scales: HAM-D, BPRS+ and Berlin Questionnaire
- Determination of subject eligibility
- Recording of adverse events

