#### As sensitivity analyses:

- a) A mixed-effect model with repeated measures (MMRM) approach will be used, under the missing at random framework carried out using an adequate contrast at Week 2 or Week 6, accordingly. The model will include fixed categorical effects of treatment group, region, visit and treatment-by-visit interaction as well as the continuous fixed covariates of mean baseline ESS. This MMRM model will be run with an unstructured correlation matrix to model the within-subject errors.
- b) MCP-Mod approach will be applied to identify the most suitable dose-response curve. Further details about the curve selection and validation procedures being used will be stated in the Statistical Analysis Plan.
- c) Similar to the primary analysis a Rank ANCOVA will be modelled in order to provide evidence of the treatment effect in case of violation of normality assumption.
- d) Primary Analysis, and sensitivity analysis as described above will be performed in the Per Protocol Population.

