9 EFFICACY ENDPOINTS

Baseline efficacy value will be defined as the last measure done prior to the randomization.

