10 STATISTICAL METHODOLOGY FOR EFFICACY ENDPOINTS

10.1 Primary Efficacy Analysis

ESS mean absolute change from baseline to the end of the 6-week treatment period will be analysed with an ANCOVA model, with the baseline ESS as a covariate, region and treatment as a factor. Least-squared (LS) absolute mean changes will be presented by treatment group along with their associated 95% CIs and 2sided p-values; these data will then provide estimated for the within arm change from baseline. The difference between each of the 3 dose arms and the placebo arms in Least-squared (LS) absolute mean changes will also be presented together with the corresponding 95% confidence interval and 2-sided p-value. These paired comparisons will be performed without any multiplicity adjustment. Also, the 4 degrees of freedom (DF) associated with the overall F-test for differences between the treatment arms will be decomposed using Type I sums of squares into three orthogonal single DF contrasts to estimate the linear, quadratic and cubic components of any potential dose response. Baseline data will be imputed with the baseline ESS average. Multiple Imputation Jumping to Reference method will be used to impute post-baseline data (see section 10.4.2 for further reference).

10.1.1 Sensitivity analyses missing reductions imputed to 0:

Same primary analysis will be repeated imputing post-baseline missing ESS evaluations to baseline data that is reduction equal to 0.

10.1.2 Sensitivity analyses MMRM Model:

A mixed-effect model with repeated measures (MMRM) approach will be used, under the missing at random framework carried out using an adequate contrast at Week 2 or Week 6, accordingly. The model will include fixed categorical effects of treatment group, region, visit and treatment-by-visit interaction as well as the continuous fixed covariates of mean baseline ESS. This MMRM model will be run with an unstructured correlation matrix to model the within subject errors. In this case missing values will not be imputed, since (MMRM) is handling missing data through the Maximum Likelihood estimation method.

Unstructured covariance matrix is assumed to explain within subject covariance in MMRM method in protecting the type I error rates. In the event if the assumption of unstructured covariance (UN) matrix results in non-convergence of the model, only then the following covariance structures will be considered in the order mentioned below.

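### The primary ANCOVA uses only the last pre-randomisation ESS; adding the screening ESS already collected as a second covariate would be a nearly free, unbiased gain in precision, of uncertain and at most modest size

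*Protocol*

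**What the plan says.** Under Protocol 11.1.4, the ESS change to week 6 "will be analysed with an ANCOVA model, with the baseline ESS as a covariate, region and treatment as a factor". Protocol 8.4.1.14.1 schedules the ESS at "screening, baseline (day -1), visit 2 (day 14), and visit 3 (day 42"), so there are two scores before treatment. The first is also an entry condition: Protocol 8.1, criterion 6, requires "Epworth Sleepiness Score (ESS) > 12 at screening". It falls in the window headed "Screening assessments (Day -28 to Day -8") in Protocol 8.4.2.

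The SAP keeps one of the two: "Baseline efficacy value will be defined as the last measure done prior to the randomization" (section 9). SAP 10.1 repeats the protocol's primary model, "with the baseline ESS as a covariate, region and treatment as a factor". The screening score therefore enters the model only when it happens to be the last one available. The MCP-Mod code in SAP 10.1.3 also has a single baseline term, and the ANCOVAs in SAP 10.2 adjust for one baseline value.

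The MMRM is less clear. Protocol 11.1.4 and SAP 10.1.2 refer to "continuous fixed covariates of mean baseline ESS", and neither says what is averaged, or whether anything is.

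**The concern.** A single ESS is a subjective self-report with measurement error, and Protocol 7.2 says as much when it relies on baseline comparison and on ANCOVA and MMRM to control that subjectivity. The same section describes the ESS recall period as weeks to months. Two scores taken one to four weeks apart should therefore describe overlapping periods and act to some degree as repeat measurements of one trait. If so, the screening score carries information about the week-6 score beyond what Day -1 carries, and leaving it out makes the confidence intervals for the dose-versus-placebo differences wider than the collected data require.

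Only precision is at stake. Both scores precede randomisation, so bias, Type I error and the estimand are the same with one covariate or two.

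**Working it through.** **1. The plan's own figure.** Inputs from Protocol 11.2 and SAP 5: difference 3.0, SD 5.0, two-sided alpha 0.05, power 80%, two-sample t-test, 50 per group.
- Normal approximation: n = 2 × (1.960 + 0.842)² × 25 / 9 = 43.6, so 44 per group. The t-test gives 45.
- Power of the t-test with 50 per group at SD 5.0 is 84.4%.
- At SD 5.3, the top of the range in Protocol 7.2, the t-test needs 50 per group, with 80.0% power.

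The stated 50 is thus reproduced at SD 5.3 and is conservative at 5.0. Neither calculation contains a covariate.

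**2. Gain without selection.** Let s, b and y be the screening, Day -1 and week-6 scores. The residual variance with s and b, divided by that with b alone, is

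1 − (r_sy − r_sb·r_by)² / [(1 − r_sb²)(1 − r_by²)].

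- All correlations equal to ρ: the ratio becomes (1 + 2ρ)/(1 + ρ)². At ρ = 0.3 it is 1.6/1.69 = 0.95; at 0.5, 2.0/2.25 = 0.89; at 0.7, 2.4/2.89 = 0.83.
- First-order decay with time (r_sb = r_by = ρ, r_sy = ρ²): the numerator is ρ² − ρ·ρ = 0, so the ratio is 1 and nothing is gained.

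**3. Gain with selection.** Entry limits the screening score to 13–24, which weakens it as a covariate. I simulated the three scores with selection at > 12, assuming an unselected SD of 4.5 and a mean of 14 or 11. None of these values is in the documents.

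| Assumed correlations | Variance ratio, mean 14 | Variance ratio, mean 11 |
|---|---|---|
| all 0.3 | 0.978 | 0.983 |
| all 0.5 | 0.947 | 0.959 |
| all 0.7 | 0.901 | 0.919 |
| all 0.8 | 0.866 | 0.887 |
| first-order decay, 0.3 to 0.8 | 1.000 | 1.000 |

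The standard error falls by 1 − √ratio. At best that is 1 − √0.866 = 6.9%. For three in-between patterns (mean 12, r_sb = 0.7, r_sy lower than r_by by 0.10 to 0.15) the ratio was 0.977 to 0.994, or 0.3% to 1.2% of the standard error.

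A second simulation used a latent trait with error in each score. Residual variance fell by 5–13% for a stable trait, 2–6% for slow drift (correlation time 180–365 days), about 1% at 90 days and about 0.2% at 45 days.

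**4. Second covariate or average.** With equal correlations, the average of the two scores does as well as the pair. Under first-order decay with selection, replacing Day -1 by the average raises residual variance by 2% to 15% (ratios 1.018 to 1.152). Two separate covariates avoid that risk.

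**5. Cost.** With 200 subjects and 7 parameters (intercept, three treatment, two region, one covariate), 193 residual degrees of freedom remain. A useless extra covariate costs about 1/193 = 0.5% of variance.

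**6. Why no power figure follows.** Suppose 5.0 is the unadjusted SD of the week-6 score and its correlation with Day -1 is 0.5, without selection. The planned model then has residual SD 5.0 × √(1 − 0.25) = 4.33, and normal-approximation power at 50 per group is already about 93%. Shrinking 5.0 itself by a variance ratio would skip this step.

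**The case against.** The strongest case on the other side is that ANCOVA on the last pre-randomisation value is a sound choice, contradicts nothing in the documents, and that a second covariate is a matter of preference. Screening lies 50 to 70 nominal days before week 6, against 43 for Day -1, so some decay of correlation is plausible, and under first-order decay the gain is nil. Imputation dilutes it further. With 15% of changes set to 0 (the Protocol 11.1.4 rule, which is a sensitivity analysis in SAP 10.1.1), the ratio moved from 0.948 to 0.958 at equal correlations of 0.5 and from 0.901 to 0.919 at 0.7. All of this stands, and it is why the lower end of the range is zero. In its favour, exact first-order decay of the observed scores leaves no room for measurement error in Day -1, which is hard to square with a subjective scale. None of it shows a harm from adding the covariate.

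Two stronger readings are tempting and are not supported.

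- A reader might infer that the screening score is thrown away for no reason. It is the eligibility gate, with a cut-off that Protocol 7.2 explains as a way to control ESS variability, and under SAP 9 it is the fallback baseline. What can be said is that no reason is stated for leaving it out of the model. It cannot even be said that the MMRM excludes it, given the undefined mean baseline.
- A reader might scale SD 5.0 or 5.3 by the variance ratio and report power rising from 84% to 86–88%, or from 79% to 81–83% with 49 per arm. Those SDs are unadjusted t-test inputs, not Day -1-adjusted residual SDs. The planned covariate is already a margin on top of them, and the SAP 6 ITT set (about 230/4 = 57 per arm before any undosed subjects) is larger than the completer count.

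**Conclusion.** The point holds as an efficiency suggestion. The plan collects two pre-treatment ESS scores for every eligible subject, models one, and does not say why. Under the assumed correlation patterns, with selection at screening ESS > 12, adding the other would lower residual variance by between about 0% (correlation decaying quickly) and about 13% (stable trait with measurement error), or 0 to 7% of the standard error. For slow drift the figure is 2–6% of variance. The documents contain no ESS correlations, so the range cannot be narrowed from them, and a gain is probable rather than certain. The present analysis needs no correction to be valid, and the sample size does not depend on the change.

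**What to change.** Before unblinding, amend Protocol 11.1.4 and SAP 10.1 as follows:
- Add the screening ESS total as a second continuous covariate beside the Day -1 ESS. Do not average the two.
- Keep change from Day -1 as the outcome.
- Use the same two covariates in the multiple-imputation model, the MMRM (replacing the undefined mean baseline ESS), the MCP-Mod model and the ESS secondary ANCOVAs.
- State how a subject without a Day -1 score is handled. SAP 9 would make the screening score that subject's baseline, so the two covariates would coincide, while SAP 9.1 imputes a missing baseline with the average.

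The cost is one degree of freedom per model and a consistent edit across several model statements. It needs no new data, visits or subjects.

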#### As sensitivity analyses:

- a) A mixed-effect model with repeated measures (MMRM) approach will be used, under the missing at random framework carried out using an adequate contrast at Week 2 or Week 6, accordingly. The model will include fixed categorical effects of treatment group, region, visit and treatment-by-visit interaction as well as the continuous fixed covariates of mean baseline ESS. This MMRM model will be run with an unstructured correlation matrix to model the within-subject errors.
- b) MCP-Mod approach will be applied to identify the most suitable dose-response curve. Further details about the curve selection and validation procedures being used will be stated in the Statistical Analysis Plan.
- c) Similar to the primary analysis a Rank ANCOVA will be modelled in order to provide evidence of the treatment effect in case of violation of normality assumption.
- d) Primary Analysis, and sensitivity analysis as described above will be performed in the Per Protocol Population.

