# 11.5. Handling of dropouts or missing data

For the primary analysis ESS missing at 6-weeks will be inputed under the treatment failure approach.

As sensitivity analyses, a mixed-effect model with repeated measures (MMRM) approach will be used, under the missing at random framework carried out using an adequate contrast at Week 2 or Week 6, accordingly. The model will include fixed categorical effects of treatment group, visit and treatment-by-visit interaction as well as the continuous fixed covariates of mean baseline ESS. This MMRM model will be run with an unstructured correlation matrix to model the within-subject errors.

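### The MMRM fits a single baseline-ESS slope and region effect across weeks 2 and 6, so its week-6 contrast need not match the ANCOVA even with no missing data: small, unbiased, cheap to remove

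*Protocol*

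**What the plan says.** **Primary analysis.** Protocol 11.1.4 and SAP 10.1 analyse the week-6 ESS change by ANCOVA "with the baseline ESS as a covariate, region and treatment as a factor". Only week-6 change enters, so the baseline slope and region effect belong to that visit. For missing week-6 values the Protocol treats the subject as a failure, "that is imputing the missing ESS reduction as 0". The SAP uses jump-to-reference multiple imputation instead.

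**MMRM.** Protocol 11.1.4 a), the synopsis and SAP 10.1.2 give the same terms: "fixed categorical effects of treatment group, region, visit and treatment-by-visit interaction as well as the continuous fixed covariates of mean baseline ESS". On covariance the Protocol says "This MMRM model will be run with an unstructured correlation matrix to model the within-subject errors". The treatment effect is "carried out using an adequate contrast at Week 2 or Week 6, accordingly". SAP 10.1.2 adds: "In this case missing values will not be imputed, since (MMRM) is handling missing data through the Maximum Likelihood estimation method".

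**Protocol 11.5** gives the model its role: "As sensitivity analyses, a mixed-effect model with repeated measures (MMRM) approach will be used, under the missing at random framework". That section lists "fixed categorical effects of treatment group, visit and treatment-by-visit interaction" plus baseline ESS, and leaves out region.

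No current description has a baseline-by-visit or region-by-visit term.

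**The concern.** If every covariate is crossed with visit, an MMRM on complete data returns exactly the week-6 estimate that the ANCOVA gives. Once data are missing, any difference between the two then comes from how the missing data are handled, which is what a missing-at-random comparator should show.

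The written MMRM lacks this property. It pools one baseline slope over weeks 2 and 6, while the ANCOVA uses the week-6 slope. If the relation of change to baseline differs between the visits, the two models adjust differently for the same chance baseline imbalance. Holding region constant across visits has the same kind of effect. Part of any gap between the analyses would then have nothing to do with missing data, and the pooled slope might cost some precision at week 6.

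**Working it through.** **Inputs from the documents** (Protocol 11.2 and SAP 5): effect 3.0, SD of change 5.0, 50 completers per arm, two-sided 0.05, withdrawal about 15%, baseline SD 3.5 and final SD 4.8 from the cited modafinil study.

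**Assumed, because the documents give none:** slope difference d between visits 0 to 0.4; week-2 SD s2 4 to 5; week-2/week-6 correlation r 0.5 to 0.7; baseline SD sb 2.5 to 3.5 (2.5 tried because entry requires ESS > 12). Week-6 residual SD s6 = 5.0.

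**The plan's own figure.** The plan states nothing about MMRM slopes. Its 50 per arm gives the reference standard error, 5.0 × √(2/50) = 1.0. The sample-size formula at SD 5.0 gives 2 × (1.960 + 0.842)² × 25/9 = 43.6, so 44 (45 by exact t). Normal-approximation power at 50 per arm is 85.1%. The stated 50 reproduces by exact t at SD 5.3, the top of the range in Protocol 7.2. The present point does not depend on this.

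**Closed form, complete data.**

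1. Weight of week 2 in the pooled slope: w = (s6² − r·s2·s6) / (s2² + s6² − 2·r·s2·s6).
2. Week-6 slope misfit: w × d.
3. MMRM minus ANCOVA contrast = misfit × (difference in arm baseline means). Its SD is w·d·sb·√(2/50).
4. Week-6 residual variance becomes s6² + (w·d)²·sb², so the standard error is multiplied by √(1 + (w·d)²·sb²/s6²).

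Worst corner (s2 = 4, r = 0.7, sb = 3.5, d = 0.4):

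- w = (25 − 14)/(16 + 25 − 28) = 11/13 = 0.846; misfit = 0.338.
- SD of gap = 0.338 × 3.5 × 0.2 = 0.237.
- Standard error factor = √(1 + 0.0561) = 1.028.

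| s2, r, sb | d | SD of gap | SE increase | Power |
|---|---|---|---|---|
| any | 0 | 0 | 0% | 85.1% |
| 5, 0.5, 2.5 | 0.2 | 0.050 | 0.12% | 85.0% |
| 4, 0.7, 3.5 | 0.2 | 0.118 | 0.70% | 84.6% |
| 5, 0.5, 2.5 | 0.4 | 0.100 | 0.50% | 84.7% |
| 4, 0.7, 3.5 | 0.4 | 0.237 | 2.77% | 83.1% |

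**Simulation, complete data** (4 × 50, three regions, REML, unstructured covariance; sb 3.5, s2 4.5, r 0.6):

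| d | SD of gap | mean absolute gap | 95th percentile | mean SE, MMRM vs ANCOVA |
|---|---|---|---|---|
| 0 | 0.041 | 0.028 | 0.094 | 1.000 vs 1.000 |
| 0.2 | 0.098 | 0.073 | 0.199 | 1.007 vs 1.002 |
| 0.4 | 0.176 | 0.137 | 0.341 | 1.015 vs 0.999 |

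With equal true slopes a small gap remains, because the estimated slopes still differ by chance and region is pooled. Mean estimates were −3.02 to −3.04 under both models, so there is no sign of bias. A further simulation of equal slopes gave an SD of 0.03. Another, set by baseline correlations of 0.5–0.7 at week 2 and 0.3–0.5 at week 6, gave SDs of 0.053 to 0.194, 95th percentiles of 0.11 to 0.40 and variance ratios of 1.000 to 1.042.

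**With the extra terms.** Adding baseline-by-visit cuts the SD of the gap to 0.008 (95th percentile about 0.02). Adding region-by-visit as well makes the gap exactly 0.

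**Scale.** If 15% of subjects in each arm have their change set to 0, a 3.0-point effect shrinks by 0.15 × 3.0 = 0.45.

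**The case against.** The strongest reply is that this is a preference and not an error. A common slope gives a valid randomised comparison, and the documents never promise that the MMRM will equal the ANCOVA on complete data. It is one of several sensitivity analyses and cannot change the primary result. That stands.

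Four stronger readings are tempting, and the documents do not support them:

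- **That the MMRM is the only check on missing data.** SAP 10.1.1 repeats the primary model with missing reductions set to 0, so only the imputation rule changes. SAP 10.1.6 repeats it with different reallocation windows. The MMRM is only the sole analysis labelled missing at random.
- **That precision is lost in any case.** The closed form gives no loss with equal slopes, and nothing in the documents says the slopes differ. Selection on a high score is weak support: the ESS > 12 criterion applies at screening, whereas the covariate is the last value before randomisation (Day -1), so some regression to the mean has already occurred. Protocol 7.2 also suggests the entry cut-off may reduce variability, and a smaller baseline SD shrinks the gap.
- **That the artefact rivals the 0.45-point dilution.** The 0.40 is an upper percentile of a random discrepancy centred on zero; the 0.45 is a systematic mean shift. They are different kinds of quantity.
- **That the missing region term in Protocol 11.5 is evidence for the slope point.** Region appears in the synopsis, in 11.1.4 and in SAP 10.1.2, so the omission is editorial.

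The reply does not remove the algebra. The two contrasts can differ for a reason unrelated to missing data, and one model term nearly eliminates it.

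**Conclusion.** The point holds as a minor matter of specification. That the contrasts need not coincide follows from the written models alone. The size rests on the assumed slopes, week-2 SD and correlations. Within those ranges the typical (mean absolute) gap is 0.03 to 0.14 points at the main simulation setting. The largest simulated SD is 0.19, and 0.24 is reached only at the corner that also gives the largest precision loss. Even there, power stays at 83% or more. A reader should not infer that the MMRM result would be biased or unusable. What it loses is a clean interpretation of small differences from the primary analysis.

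**What to change.** In Protocol 11.1.4 a), Protocol 11.5, the synopsis copy and SAP 10.1.2, add a baseline ESS-by-visit interaction to the MMRM. List region in Protocol 11.5 as in 11.1.4.

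Optionally add region-by-visit. This makes the complete-data contrasts identical, but in the simulations it removed only about a further 0.01 to 0.02 points. More imbalance of regions between arms would leave more to remove.

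Cost: one degree of freedom for baseline-by-visit, plus the number of region categories minus 1 if region-by-visit is added. That number is not fixed at three, because SAP 10.4.1 merges regions with fewer than 20 patients and lets a site with 20 or more stand as its own category. No new data are needed and the primary analysis is unchanged.
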